5.4.2 Withdrawal of Subjects from Study Visits

Subjects may voluntarily withdraw from study participation at any time without having to provide a reason. Subjects may be withdrawn because of the appearance of a new health condition which may require care or medications prohibited by the protocol, unacceptable AEs, refusal to continue treatment, or at the Investigator's discretion if it is in the subject's best interest.

If a subject withdraws from the study at any time either at his or her request or at the Investigator's discretion, the reason(s), including the primary reason for withdrawal, if provided by the subject, should be recorded. Subjects who discontinue the study prematurely should undergo all End of Study assessments, if possible.

Subjects may be withdrawn by the Investigator and their study participation discontinued prematurely for several reasons. Discontinuation from the study is **mandatory** in the following circumstances:

- The subject requires blood transfusion or ESA treatment (e.g. for excessive acute bleeding) or intake of iron preparations other than the study drug. If possible, discontinuation assessments should take place before transfusion or treatment. The reason for discontinuation and the date must be recorded on the appropriate page of the case report form (CRF). The date on which the procedure actually took place should also be recorded on the CRF.
- Surgery with expected significant blood loss.
- Development of an illness, condition, or procedural complication, which would interfere with the subject's continued participation.
- The Investigator/study physician feels it is medically in the best interest of the subject to discontinue the subject's participation in the study.
- Pregnancy (to be recorded on the specific pregnancy reporting form).

Subjects may be discontinued from the study for the following reasons (reason to be recorded on the appropriate page of the CRF):

- Subject does not comply with study procedures.

Appropriate documentation will be kept for all subjects who are enrolled into the study (i.e., who provide written informed consent). All subjects who discontinue from the study will be strongly encouraged to have all assessments for the End of Study visit (Visit 6) performed.

If a subject refuses to continue in the study, the reason for refusal must be fully documented in the subject's source document and recorded in the study-specific CRF. It is the subject's right to withdraw from the trial without providing a reason. In this case, the source documents and the CRF must document the reason for discontinuation as "withdrawal by subject".

It is essential to obtain follow-up data on any subject withdrawn because of an AE. In any case, every effort must be made to undertake protocol-specified safety follow-up procedures. If a subject is discontinued due to an AE, the event must be followed-up by the investigator through contact with the subject until resolution or stabilisation has occurred. All AEs must be followed-up until resolution, stabilisation or the subject is lost to follow-up and cannot be contacted.

Reasons for discontinuations will be documented in the CRFs. Subjects who discontinue prematurely will not be replaced.

The Sponsor may discontinue the study for any reason at any time. In this case, all subjects, after a final visit, will be withdrawn from the study and study treatment discontinued.

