7.7 Prohibited Therapy and Concomitant Treatment

Prohibited therapies in this study will include the following drugs:

- Oral or other IV iron therapy (other than the study medication). Note: Ongoing use of multivitamins or nutritional supplements containing iron are permitted when doses are lower than 75 mg per day. If the dose of iron in these products is unknown, they should not be administered during the study.
- ESAs
- Blood transfusions

Note: Blood transfusions and ESAs might be used as rescue medication if the subject requires such treatment for symptomatic anaemia therapy. In this case, the subject must be withdrawn from the study and end of study procedures must be completed before transfusion or treatment. The reason for discontinuation and the date must be recorded on the appropriate page of the CRF. The date on which the procedure actually took place must also be recorded in the CRF.

If symptoms of acute iron intoxication occur, treatment will be according to standard medical practice, e.g. consider the use of an iron chelator such as deferoxamine mesylate.

In case of hypersensitivity reactions (including anaphylactoid reactions) or signs of intolerance, an appropriate therapy will be started according to the Investigator's judgement.

Any concomitant treatment given for any reason during the course of the study must be recorded on the CRF and in the subject's medical records, including dosage, start and stop dates and reason for use.

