3.3 Per Protocol Set

The Per-Protocol Set (PPS) is defined as all subjects in the FAS with a study drug compliance between 80 and 120% and do not have any major protocol violations ([appendix 1](#)).

The subjects in the PPS will be analysed based on the treatment that they were randomised to.

As per protocol, blood samples had to be drawn before study drug administration (when planned). All laboratory efficacy assessments (Hb, Ferritin, and TSAT) that are measured from a blood sample

taken after the study drug administration will not be considered for any efficacy analysis for both PPS and FAS. The subjects will still be in the PPS if they do not have a major protocol deviation.

For subjects who took prohibited concomitant medication, all laboratory efficacy assessments (Hb, Ferritin, and TSAT) will be censored after the prohibited medication start date for both PPS and FAS. The subjects will still be in the PPS if they do not have a major protocol deviation.

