STUDY DRUG DEVIATION	STUDY DRUG DEVIATION # 1	Incorrect IMPs storage condition (FCM store > 30°C or freeze / IS store < 4°C or > 25°C or freeze)	TBD*
	STUDY DRUG DEVIATION # 2	Incorrect treatment administration vs randomization	Major
	STUDY DRUG DEVIATION # 3	Study drug not stopped when subject experienced any kind of hypersensitivity reaction related to the study drug during administration	Major

Vifor DVSCAT (Categories of PDs)	Vifor DVDECOD (Sub-Categories of PDs)	Details	Major or Minor
PROHIBITED MEDICATION	PROHIBITED MEDICATION	Prohibited Therapy and Concomitant Treatment (Oral or other IV iron therapy (other than the study medication), multivitamins or nutritional supplements containing iron > 75 mg per day, ESAs, Blood transfusions)	Major
PROCEDURE/TEST NOT DONE	PROCEDURE/TEST NOT DONE # 1	Vital Signs missing	Major
	PROCEDURE/TEST NOT DONE # 2	Physical Examination missing (Fully missing is Major at Screening/Fully missing is Minor at EOS/Partially missing is Minor at Screening and EOS)	Major/Minor
	PROCEDURE/TEST NOT DONE # 3	Laboratory tests: Haematology & Iron status missing from Visit 2 to Visit 6(Missing assessment is major/Missing parameter is minor)	Major/Minor
	PROCEDURE/TEST NOT DONE # 4	Laboratory tests: Haematology & Iron status missing at Visit 1(Missing assessment is major/Parameters Hb, MCH, MCV, MCHC, Serum Ferritin, TSAT missing is major/Other parameters missing is minor)	Major/Minor
	PROCEDURE/TEST NOT DONE # 5	Laboratory tests : Chemistry missing from Visit 2 to Visit 6 (Missing assessment is major/Missing parameter is minor)	Major/Minor
	PROCEDURE/TEST NOT DONE # 6	Laboratory tests: Chemistry missing at Visit 1(Missing assessment is major/Parameters CRP, ALT, AST missing is major /Other parameters missing is minor)	Major/Minor
	PROCEDURE/TEST NOT DONE # 7	Laboratory tests at planned visits: Urinalysis missing (Missing assessment is major/Missing parameter is minor)	Major/Minor
	PROCEDURE/TEST NOT DONE # 8	Laboratory tests: Hepatitis B and C missing at Visit 1 (Any parameters missing is major)	Major
	PROCEDURE/TEST NOT DONE # 9	ECG missing	Minor
	PROCEDURE/TEST NOT DONE # 10	Laboratory tests: Pregnancy Test at Screening missing	Major
	PROCEDURE/TEST NOT DONE # 11	Laboratory tests: Pregnancy Test at Visit 6 missing	Major
PROCEDURE OUTSIDE WINDOW	PROCEDURE OUTSIDE WINDOW # 1	Laboratory tests Out Of planned Window	Minor
	PROCEDURE OUTSIDE WINDOW # 2	Vital Signs out of planned window	Minor

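### SAP 3.3 keeps efficacy laboratory values dated on the day of rescue, so a post-transfusion Hb can score a rescued subject as a responder in the FAS; Protocol 5.4.2 and 7.7 conflict on whether such a sample may arise

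*Protocol*

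**What the plan says.** **Timing of the last blood draw.** Protocol 5.4.2 makes discontinuation mandatory when a subject requires transfusion, ESA treatment or other iron, and gives excessive acute bleeding as an example. It then says "If possible, discontinuation assessments should take place before transfusion or treatment". Protocol 7.7, on transfusion and ESA rescue, says "the subject must be withdrawn from the study and end of study procedures must be completed before transfusion or treatment".

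**What is recorded about rescue.** Both sections ask for a date: "The date on which the procedure actually took place should also be recorded on the CRF" (5.4.2) and "The date on which the procedure actually took place must also be recorded in the CRF" (7.7). Neither asks for a clock time.

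**Censoring.** For subjects who took prohibited medication, SAP 3.3 says that Hb, ferritin and TSAT values "will be censored after the prohibited medication start date for both PPS and FAS".

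**PPS membership.** SAP 3.3 requires "study drug compliance between 80 and 120% and do not have any major protocol violations". SAP Appendix 1 grades prohibited therapy as Major, and its list includes "multivitamins or nutritional supplements containing iron > 75 mg per day, ESAs, Blood transfusions". Yet after the censoring rule SAP 3.3 adds: "The subjects will still be in the PPS if they do not have a major protocol deviation".

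**Endpoint and sets.** Response is an Hb rise of at least 2 g/dL from baseline at any time up to Week 8 (SAP 2.6.1). The PPS is primary and the FAS is a sensitivity analysis (SAP 4.1.6), but SAP 4.6.1 applies the non-inferiority test to both. SAP 4.1.8 imputes no missing efficacy data, and no section classes a rescued subject as a non-responder.

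**The concern.** A value dated on the rescue start date is not after that date, so the literal rule keeps it. If the transfusion came first and the end-of-study sample followed the same day, the retained Hb reflects donor blood. SAP 4.1.3 re-maps every assessment into an analysis window, so an early-termination sample is available to the endpoint, and one qualifying value is enough.

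The same section of the SAP treats study drug more strictly: a sample drawn after dosing is excluded by order of sampling, not by calendar date. Rescue, which can raise Hb directly, has the looser rule.

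If FCM were the less effective arm it could be expected to need more rescue. The error would then run towards a false non-inferiority finding, in the analysis meant to check the PPS result. The same gap lets TSAT and ferritin drawn just after non-study IV iron count towards the secondary iron-correction endpoint.

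A transfusion may also be recorded as a procedure. SAP 4.4 and 4.7.5.1 list procedures separately from medications, so such a record may have no prohibited-medication start date to trigger censoring at all.

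**Working it through.** **1. The plan's own figures.** Inputs (Protocol 11.2): 70% response in both arms, margin 15 points, one-sided 2.5%, 80% power, 20% drop-out.

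- n per arm = (1.960 + 0.842)² × 2 × 0.70 × 0.30 / 0.15² = 146.5, so 147; power at 147 is 80.1%.
- 147 / 0.80 = 183.75, so 184 per arm and 368 in total. Both stated figures reproduce.

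**2. Rules side by side, for a rescued subject without an earlier response.**

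| Sample | SAP 3.3 as written | Can it score a response in the FAS? |
|---|---|---|
| Before rescue, any day | kept | yes, correctly |
| After rescue, same date | kept | yes, wrongly |
| After rescue, later date | censored | no |

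Only the middle row is at fault. With dates alone, the SAP cannot separate it from a same-day sample drawn before rescue.

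**3. Weight of one subject.** 100/184 = 0.54 points. The FAS has at most 184 per arm, because it requires a dose and a post-baseline value. At 147 per arm it would be 100/147 = 0.68 points, which applies only if rescued subjects stay in the PPS.

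**4. At the decision boundary.** Using the planned Newcombe interval with continuity correction and IS at 129/184 (70.1%):

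- FCM 119/184: lower bound −15.23%, fails.
- FCM 120/184: lower bound −14.68%, passes.

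One subject changes the result only there.

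**5. Chance of a false non-inferiority finding.** Assume a true difference exactly on the margin, 55% FCM v 70% IS, with 184 per arm. Sum the binomial probabilities of all outcomes whose lower bound exceeds −15%, after adding k mis-scored responders. The documents give no rescue rate, so k from 0 to 3 is an assumption.

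| k | FCM only | Same k in both arms |
|---|---|---|
| 0 | 2.2% | 2.2% |
| 1 | 2.9% | 2.25% |
| 2 | 3.7% | 2.3% |
| 3 | 4.7% | 2.3% |

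A normal approximation, Φ((k/184)/SE − 1.96) with SE² = [p(1 − p) + 0.70 × 0.30]/184 and p = 0.55 + k/184, gives 2.5%, 3.2%, 4.1% and 5.1% for FCM only. The exact figures are lower because the planned interval is slightly conservative.

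**The case against.** Protocol 7.7 requires end-of-study procedures to be finished before rescue. At a site following it, a same-day sample is a pre-rescue sample, and keeping it is right. SAP Appendix 1 grades transfusion, ESAs and other iron as Major, which takes the subject out of the PPS and so out of the primary analysis. The case also needs several things together: rescue, blood drawn after it on the same date, Hb then at least 2 g/dL above baseline in someone rescued for bleeding or symptomatic anaemia, and no earlier response. For Hb it is in practice confined to transfusion, since an ESA or iron dose would not plausibly raise Hb by that much within a day.

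Most of this stands, and it rules out two stronger readings. A reader might infer that the protocol simply accepts post-rescue blood. It does not: one section forbids for transfusion and ESA rescue what another allows. A reader might also infer that the primary result is directly exposed. On the plain text of Appendix 1 it is not. Some doubt remains because SAP 3.3 applies the censoring to the PPS and provides for such subjects to remain there, which fits poorly with a blanket Major grade. The documents do not say whether rescue carried out as 7.7 permits is logged as a deviation.

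The objection does not remove the gap in the FAS. A site following 5.4.2 can produce the sample, and the SAP has no rule to exclude it.

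Simply deleting every untimed same-day value would also do harm. It could discard the draw that 7.7 requires. If that were the subject's only post-baseline value, an early failure would leave the FAS, because FAS entry needs a post-baseline value and nothing is imputed.

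**Conclusion.** The point holds as a minor one, for the FAS. SAP 3.3 retains same-day post-rescue values, Protocol 5.4.2 and 7.7 disagree on whether they may occur, and nothing scores rescue as non-response. A rescued failure can therefore count as a responder in the supporting non-inferiority analysis. The PPS is affected only if permitted rescue is not logged as Major.

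The size is 0.54 points per subject. The rise from 2.2% to 4.7% is a worst case: three mis-scored subjects, all in FCM, at a true difference exactly on the margin. It should not be read as the expected inflation. Equal numbers in both arms leave the rate at about 2.3%, and an excess in the IS arm would work against FCM. The rescue rate and its split between arms are unknown, so neither the direction nor the amount can be predicted from the documents. The sample size is unaffected.

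**What to change.** 1. In SAP 3.3, state that *Hb, TSAT and ferritin values dated on or after the start date of a prohibited medication or transfusion, whether recorded as a medication or as a procedure, cannot count as a response or as iron correction unless the sample is documented as taken before rescue.*
2. Add that a subject whose only post-baseline value is an untimed same-day sample stays in the FAS as a non-responder.
3. State in the SAP whether rescue carried out under Protocol 7.7 is logged as the Major deviation in Appendix 1, so that PPS status is settled.
4. Reconcile Protocol 5.4.2 with 7.7 on the order of end-of-study assessments and rescue.

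The cost is a few sentences in the SAP, one programming condition that reads both medication and procedure records, and a protocol clarification. Because only the date of rescue is required, the exemption works only where the order was documented. The downside is that a few genuine same-day pre-rescue responses without a documented time would not be counted.

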6. RANDOMISATION, BLINDING AND UNBLINDING PROCEDURES

6.1 Randomisation

An Interactive Response Technology (IRT) system will be used in the study. A separate user manual that outlines the details of IRT will be provided to the sites.

All subjects screened must be identifiable throughout the study and will be given a unique study subject number. Each site will be identified by a 3 digit number, and subject numbering will be assigned by IRT. The Investigator will maintain a list of subject numbers and subject names to enable records to be matched at a later date.

Randomisation of eligible subjects will be performed before start of treatment with study drug. Randomisation will be performed based on a pre-defined, computer generated randomisation list. The subjects will be randomised 1:1 to receive either FCM administration(s) or IS. IRT will be contacted for treatment assignment following confirmation of eligibility at the Baseline visit.

6.2 Blinding

Due to the differences in posology between the study drug (FCM) and the comparator (IS) more injections/infusions may be required for subjects receiving IS.

Therefore, the study will utilise an open-label design to avoid unnecessary IV placebo injections/infusions. This reduces the burden of requiring additional subject visits to both groups as well as removing potential infections and other side-effects that may result from a placebo IV injection/infusion.

6.3 Unblinding

As this is an open-label study, unblinding procedures are not applicable.

7. STUDY TREATMENTS

7.1 Dosage Forms/Formulation

All investigational medicinal products used in this study have been manufactured in accordance with current Good Manufacturing Practice (GMP).

7.1.1 Ferric Carboxymaltose

Ferric carboxymaltose will be provided by Vifor Pharma – Vifor (International) Inc. for this study.

Strength:	Sterile FCM solution as a 5% w/v iron solution in water for injection.
Excipients:	
Appearance:	Dark brown, non-transparent aqueous solution.
Dosage Form:	10 mL vials containing 500 mg iron per vial.
Manufacturer:	Vifor Pharma – Vifor (International) Inc., Switzerland.
Storage:	
Note:	For drip infusions, FCM must be diluted only in sterile 0.9% sodium chloride solution.

7.1.2 Iron Sucrose

Iron Sucrose (Venofer) will be provided by Vifor Pharma – Vifor (International) Inc. for this study.

Strength:	Sterile solution for injection containing 2% w/v iron. 1 mL of Venofer contains 20 mg of iron.
Excipients:	Water for injection, sodium hydroxide (for pH adjustment).
Appearance:	Dark brown, non-transparent aqueous solution.
Dosage Form:	5 mL ampoules containing 100 mg iron per ampoule.
Manufacturer:	Vifor Pharma – Vifor (International) Inc., Switzerland.
Storage:	Store between 4°C and 25°C. Do not freeze.

7.2 Drug Dosage and Administration

7.2.1 Arm A: Ferric Carboxymaltose

Study drug should be administered in doses based on subject BW and Hb value at screening as per Table 2.

Subjects will receive study drug as undiluted injection or infusion. The individual dose requirement (in mg of iron) per visit is described below:

Table 2: FCM Dosing Schedule

	Total Iron (mg) as FCM				
	BW 35 - <70 kg ¹		BW ≥70 kg		
	Hb <10 g/dL	Hb ≥10- <14 g/dL	Hb <10 g/dL	Hb ≥10- <14 g/dL	
Day 1	1,000 mg	1,000 mg	1,000 mg	1,000 mg	
Day 8	500 mg	No dose	1,000 mg	500 mg	

Notes: BW = Body weight; FCM = Ferric carboxymaltose; Hb = Haemoglobin.

1. The maximum single dose that should be given to a subject is 20 mg/kg BW, therefore for subjects with BW 35 - <50kg and Hb ≥ 10 g/dL, the 1,000 mg dose should be split into 2 x 500 mg (one 500 mg dose on Day 1 and one 500 mg dose on Day 8. Subjects with BW 35 - <50 kg and Hb < 10g/dL should receive 3 doses of 500 mg (on Day 1, 8 and 15).

For IV injection, the required amount of FCM solution will be drawn from the vial into a syringe and injected as an undiluted solution.

For drip infusion, FCM solution must be diluted only in sterile 0.9% m/V sodium chloride solution (500 mg iron diluted in 100 mL 0.9% w/v physiological saline, for a total volume of 110 ml or 1,000 mg iron diluted in 250 mL 0.9% w/v physiological saline, for a total volume of 270 ml). For stability reasons, dilutions to concentrations less than 2 mg iron/mL are not permitted.

From a microbial point of view, FCM preparations for parenteral administration must be used immediately after dilution with sterile 0.9% m/V sodium chloride solution.

For both injection and infusion, FCM should be administered up to a maximum single dose of 1,000 mg iron (up to a maximum of 20 mg/kg BW) over at least 5 minutes for the 500 mg dose and over at least 15 min for the 1,000 mg dose. Administration time should not exceed 30 minutes for either the 500 or the 1,000 mg dose.

7.2.2 Arm B: Iron Sucrose

For subjects in the individually calculated IS dosage regimen group, the individual iron deficit will be calculated using the formula of Ganzoni [9]:

Cumulative iron deficit [mg] =

$$BW [kg] \times (\text{target Hb}^{(1)} - \text{actual Hb}) [g/dL]^{(2)} \times 2.4^{(3)} + 500 \text{ mg}^{(4)}$$

⁽¹⁾ Target Hb for BW >35 kg = 15 g/dL, respectively 9.3 mmol/L

⁽²⁾ To convert mmol/L to g/dL: multiply Hb (mmol/L) by the factor 1.61145

⁽³⁾ Factor 2.4 = 0.0034 (iron content Hb = 0.34%) x 0.07 (blood volume = 7% of BW) x 10,000 (conversion g/dL to mg/L)

⁽⁴⁾ Iron storage depot

Note: BW = Body weight.

The calculated cumulative IS dose is to be rounded up or down to the nearest 200 mg.

Subjects will receive single doses of IS of up to a maximum single dose of 200mg iron three times a week. Depending on the calculated iron deficit, up to 11 IS injections will be given.

Iron Sucrose (Venofer) will be administered by slow IV push injection at a rate of 1 ml undiluted solution per minute (10 ml of the product in at least 10 minutes; administration time should not exceed 60 minutes) or by drip infusion in a dilution of 1 ml of Venofer in maximum 20 ml 0.9% w/v physiological saline (10 ml of the product in maximum 200 ml saline). Venofer must be used immediately after dilution. The drip infusion rate should be 200 ml solution in at least 30 minutes, and should not exceed 60 minutes.

7.2.3 IV Administration of Drug (Both Arms)

Study personnel responsible for study drug application will apply a tourniquet, seek a suitable vein, disinfect injection site and perform the vein puncture. It is recommended to use a blue catheter 22 gauge (or pink catheter 20 gauge) and secure it with duct tape. The use of blue butterfly needle is possible.

After the puncture, the correct position of the needle can be reviewed in the vein by flushing with 10 mL NaCl 0.9%. Connect the syringe or infusion set to the needle and slowly inject or infuse the FCM (see Section 7.2.1, Arm A: Ferric Carboxymaltose) or IS (see Section 7.2.2, Arm B: Iron Sucrose). The vein should then be flushed with 5-10 mL saline.

Study medication should only be administered when staff trained to evaluate and manage anaphylactic reactions are immediately available, in an environment where full resuscitation facilities can be assured. Each subject should be observed for adverse effects during and for at least 30 minutes following each injection. Hospitalisation for study drug administration is not a requirement of the study. However, Investigators might choose to hospitalise subjects while they receive study drug as a precautionary measure. Hospitalisation for this purpose does not fulfil the criteria of a serious adverse event (SAE) and will not be recorded as such. If an AE/SAE occurs before, during or after administration of study drug during

hospitalisation, this shall be assessed and recorded as per seriousness criteria for AE/SAEs.

Since FCM has a physiological pH, pain at the injection site is very unlikely, therefore caution should be given to avoid paravenous injections. The choice of an appropriate needle for the IV access should minimise the potential risk of a paravenous injection of FCM or IS. Iron Sucrose has a basic pH and therefore, if paravenous leakage occurs, a burning sensation is felt by the subject.

Treatment administration of FCM or IS must be discontinued immediately if swelling (paravenous injection) is observed, which can cause irritation and a brown discolouration of the skin which can be long-lasting. No rinsing or pressure bandage should be used, in order to prevent distribution and extension of extravasations. Study treatment can be re-administered in a different location (i.e. other arm).

